3.7. Drugs Used in the Study

3.7.1. Investigational Product

A more detailed description of pridopidine administration procedures is given in Section 5.1.

This is an uncontrolled study with no other study drug.

Additional details may also be found in the current version of the IB for pridopidine.

3.8. Drug Supply and Accountability

3.8.1. Drug Storage and Security

All medication supplied in connection with this study must be used only for this study and no other purpose.

Study drug supplies will be stored securely according to the manufacturer's drug product stipulation in a temperature-controlled storage area (a locked cupboard or pharmacy with limited access). Only authorized personnel will have access to the study drug. The study site personnel at each site will be responsible for correct storage and handling of the study drug.

All study drug supplies must be stored in a dry place, at room temperature (15°C to 25°C/59°F to 77°F). Medication must not be refrigerated.

Any actual or suspected theft or diversion must be reported to the sponsor immediately.

3.8.2. Drug Accountability

Each study drug shipment will include a packing slip listing the contents of the shipment, drug return instructions, and any applicable forms. Distribution of study drugs will be performed under the sponsor's responsibility.

The investigator is responsible for ensuring that deliveries of study drug and other study materials from the sponsor are correctly received, recorded, handled and stored safely and properly in accordance with the CFR or local regulations, and used in accordance with this protocol.

If the study drug supplies appear to be damaged or missing upon arrival at the investigational site, the sponsor should be contacted immediately.

Patients will be instructed to return all used empty bottles and unused study drug at each visit.

A record of study drug accountability (i.e., study drug and other materials received, used, retained, returned, or destroyed) must be prepared and signed by the principal investigator or designee, with an account given for any discrepancies. Empty, partially used, and unused bottles of study drug will be destroyed or returned to the sponsor or its designee. The Monitor is responsible for the accountability of the returned study drugs.

3.9. Duration of Patient Participation and Justification

This study will consist of an up to 2-week screening period, an open-label treatment period of 104 weeks and an end-of-study visit (at week 106). Patients are expected to participate in this study for its entire duration. See Section 12.4 for the definition of the end of the study.

3.10. Stopping Rules and Discontinuation Criteria

There are no formal rules for early termination of this study.

During the conduct of the study, SAEs will be reviewed (see Section 7.1.5) as they are reported from the investigational center to identify safety concerns. The study may be terminated by the sponsor at any time.

A patient may discontinue participation in the study at any time for any reason (eg, lack of efficacy, consent withdrawn, and adverse event). The investigator and/or sponsor can withdraw a patient from the study at any time for any reason (eg, protocol violation or deviation as defined in Section 11.1.2, noncompliance, or adverse event).

3.10.1. Discontinuation of Individual Patients

If hypokalemia is observed, dosing will be interrupted and should not be started again until normal electrolyte values are confirmed and maintained for 7 days. Patients needing more than 14 days to reach stable potassium levels, without study drug, should be withdrawn from the study drug. The patient will be asked to continue in the study and follow the visit schedule as outlined in the protocol.

At any visit, if a QTcF of >500 msec is recorded in a single measurement, 2 additional measurements will be performed and the mean value will be calculated. If the mean value is above >500 msec, the patient should be withdrawn from the study.

If the local ECG reading results at the site match the above criterion, the patient should stop taking study medication until the central ECG reader's report is received. If the central reader does not report a QTcF interval that would lead to discontinuation according to the above, then the patient should restart study medication.

Patients should also be discontinued if:

- they experience a seizure or convulsions (regardless of the relationship to treatment);
- their body weight decreases to <50 kg (may be discontinued based on Investigator or Sponsor discretion);
- and/or if creatinine clearance decreases to <60 mL/min (calculated using the Cockcroft-Gault equation). It is allowed to repeat the test once, if clinically appropriate.
- they experience adverse event/serious adverse event of suicide ideation or attempt; or
- they have a C-SSRS suicidal ideation score >2 (ie, 3, 4 and 5); or
- they have a C-SSRS report of suicidal act; or
- they have a PBA-s suicidal ideation item score >2 (ie, 3, 4, 5) .

Patients who discontinue study medication due to safety or tolerability reasons may continue in the study off drug and perform the scheduled visits and assessments.

In case the 45 mg bid treatment arm in PRIDE-HD is discontinued for safety reasons, the Open-PRIDE-HD study (utilizing the same 45 mg bid dose) will be stopped.

3.11. Source Data Recorded on the Case Report Form

All patient data must have supportive original source documentation in the medical records, or equivalent, before they are transcribed onto the case report form (CRF). Data may not be recorded directly onto the CRF and considered as source data unless the sponsor provides written instructions specifying which data are permitted to be recorded directly onto the CRF.

If data are processed from other institutions (eg, clinical laboratory, central image center, electronic diary data), the results will be sent to the investigational center, where they will be retained but not entered into the CRF unless otherwise noted in the protocol. These data may also be sent electronically to the sponsor (or organization performing data management) for direct entry into the clinical database (see Section 13.1). All data from other institutions will be available to the investigator.

The CRFs are filed in the sponsor's central file.

3.12. Study Procedures

Study procedures and assessments with their timing are summarized in [Table 1](#).

Detailed by-visit information is provided in the sections following the table. Detailed descriptions of each assessment are provided in Section 6 (efficacy assessments), Section 7 (safety assessments), and Section 8 (pharmacokinetic and other assessments).

Table 1: Study Procedures and Assessments

Study period	Open label treatment period											Follow Up
Visit number	V1	V2	V3	V4	TC	V5	TC	V6	V7	V8 End-Of- Treatment Visit	V9 End-Of- Study / ET Visit	
Procedures and assessments	Screening ^{a b}	Baseline ^c	Week 4 ^d	Week 12 ^d	Week 18	Week 26 ^d	Week 38	Week 52 ^d	Week 78	Week 104	Week 106 ^d	
Allowed time windows	Up to 2 weeks		±3 days	±4 days	±14 days	±14 days	±14 days	±14 days	±14 days	±14 days	±14 days	±14 days
On-site visit	X	X	X	X		X		X	X	X	X	
Telephone call					X		X					
Informed consent	X											
Medical and psychiatric history ^c	X											
Prior medication history ^c	X											
Inclusion and exclusion criteria	X	X										
Clinical laboratory tests (Clinical chemistry, hematology and urinalysis)	X	X	X	X		X		X	X	X	X	
Brief physical examination ^{f g}	X	X	X	X		X		X	X	X	X	
Electrocardiography	X ^h	X	X	X		X		X	X	X	X	
Vital signs measurement ⁱ	X	X	X	X		X		X	X	X	X	
Serum/urine β-HCG test for women of childbearing potential	X ^j	X ^k	X	X		X		X	X	X	X	
C-SSRS	X ^l	X	X ^m	X ^m	X	X ^m	X	X ^m	X	X	X ^m	
UHDRS-TMS	X	X	X	X		X		X	X	X	X	
UHDRS-TFC		X				X		X	X	X	X	
mPPT		X		X		X		X	X	X	X	
SF-12		X				X		X	X	X	X	
PBA-s	X	X	X	X		X		X	X	X	X	

Clinical Study Protocol with Amendment 02

Study period	Open label treatment period											Follow Up
Visit number	V1	V2	V3	V4	TC	V5	TC	V6	V7	V8 End-Of- Treatment Visit	V9 End-Of – Study / ET Visit	
Procedures and assessments	Screening ^{a b}	Baseline ^c	Week 4 ^d	Week 12 ^d	Week 18	Week 26 ^d	Week 38	Week 52 ^d	Week 78	Week 104	Week 106 ^d	
Allowed time windows	Up to 2 weeks		±3 days	±4 days	±14 days	±14 days	±14 days	±14 days	±14 days	±14 days	±14 days	±14 days
On-site visit	X	X	X	X		X		X	X	X	X	
Telephone call					X		X					
Abbreviated PBA-s					X ⁿ		X ⁿ					
Q-motor ^o		X						X	X	X	X	
Adverse event inquiry	X	X	X	X	X	X	X	X	X	X	X	
PK sampling ^p												
Dispense/collect study drug		X	X	X		X		X	X	X ^q		
Dosage review and adjustment (titration)		X ^r										
Concomitant medication inquiry	X	X	X	X	X	X	X	X	X	X	X	
Benzodiazepines and antidepressants inquiry ^s	X	X	X	X	X	X	X	X	X	X	X	
Alcohol/Illicit drug use inquiry	X	X	X	X	X	X	X	X	X	X	X	
Inform patients of study restrictions and compliance requirements	X	X										
Review of study compliance and adherence			X	X	X ^t	X	X ^t	X	X	X	X	

^a The screening visit of the Open-PRIDE study may coincide with the follow-up visit of PRIDE-HD. If found operationally convenient and effective for a site, the screening visit may take place over the course of more than 1 day; however, the allowed 2-week screening period may not be exceeded.

^b If a certain procedure or assessment was completed for the PRIDE-HD study, which took place on the same day as the Open-PRIDE screening visit, this procedure or assessment does not need to be repeated for Open-PRIDE.

^c All baseline (Visit 2) assessments must take place on the same day.

^d If found operationally convenient and effective for a site, the procedure and assessment visits (V3 through End of Study/ ET) may be performed over several days, as long as they are completed within the defined visit window.

Clinical Study Protocol with Amendment 02

- ^c A gap of up to 3 months is allowed between the patient's completion of the PRIDE-HD study and the Open-PRIDE screening visit. If less than 3 months have passed, and there are no changes to psychiatric, medical, or medication history since completion of the PRIDE-HD study, these data do not have to be re-captured in the eCRF. If the gap is between 3-6 months, the information has to be re-captured.
- ^f Weight will be measured at the screening visit and at baseline (for study eligibility) and at week 26, 52, 78, 104 and 106.
- ^g Brief physical exam will be focused on general appearance, the cardiovascular, pulmonary, abdominal exams, as well as directed towards any patient-reported symptoms. The brief neurological exam includes observation for cerebellar (intention) tremor and for non-cerebellar tremors (eg, resting or positional), finger-nose, heel-shin, Romberg, tandem walking, positional, and gaze-evoked nystagmus.
- ^h ECGs will be performed in triplicate at screening.
- ⁱ Vital signs include pulse, blood pressure (supine and standing), body temperature.
- ^j Serum B-HCG test will be performed for all women of childbearing potential at screening.
- ^k Urine HCG tests will be performed for all women of childbearing potential at all subsequent visits.
- ^l If less than 3 months have passed since the patient's completion of the PRIDE-HD protocol and the Open-PRIDE screening visit, the "since last visit" version of the scale can be used. If 3-6 months have passed, the screening/baseline version of the scale should be administered.
- ^m The "Since Last Visit" version will be administered at all subsequent visits.
- ⁿ The safety telephone calls will include an abbreviated PBA-s (a subset of PBA-s questions on depressed mood, suicidal ideation, anxiety, irritability, loss of motivation, and obsessive-compulsive behaviors).
- ^o Including digitomotography (speeded index finger tapping), dysdiadochomotography (pronation/supination hand tapping), manumotography and choreomotography (grip force and chorea analysis) and pedomotography (speeded foot tapping).
- ^p PK samples will be aimed to be drawn, to the extent possible, in the event of a SAE, an AE leading to discontinuation, or for patients who withdrew prematurely because of lack of efficacy.
- ^q At the end-of-treatment (EoT) visit (Visit 8), study drug will only be collected.
- ^r Patients will undergo a 1-week titration in which a pridopidine dose of 22.5 mg bid (total daily dose 45 mg) will be taken. From week 2 onwards, patients will receive a pridopidine dose of 45 mg bid (total daily dose 90 mg). Doses up to 112.5 mg bid are currently being investigated in the ongoing PRIDE-HD study. Following availability of PRIDE-HD results, the dose administered in this study may be adjusted.
- ^s This information will be collected as part of concomitant medication inquiry.
- ^t Study adherence will be reviewed during the safety telephone calls.

Abbreviations: bid=twice daily; β -HCG=beta human chorionic gonadotropin ; C-SSRS=Columbia-Suicide Severity Rating Scale; ET=Early Termination; mPPT=Modified Physical Performance Test; PBA-s=Problem Behaviors Assessment-Short form; PK=pharmacokinetic(s); Q26=every 26 weeks after the Month 12 visit; TC=telephone contact; TFC=Total Functional Capacity; TMS=Total Motor Score; SAE=serious adverse event; SF-12=Short Form 12; Q-motor=Quantitative motor; UHDRS=Unified Huntington's Disease Rating Scale; V=Visit

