3.4. Safety and Tolerability Measures and Time Points

The following safety and tolerability measures will be assessed during the study:

- AEs – will be monitored at every study visit.
- Vital signs assessments – will be monitored at every study visit.
- Concomitant medication usage - will be monitored at every study visit.
- Physical examination findings – brief physical examination will be performed at every study visit.
- Clinical laboratory evaluations (hematology, clinical chemistry, and urinalysis) - will be performed at each study visit

- ECG findings – ECG will be performed at every study visit (in triplicate at baseline; single measurement at all subsequent visits)
- Suicidality (C-SSRS and PBA-s) will be assessed throughout the study.

Tolerability endpoints:

- Proportion of subjects (%) who prematurely discontinued from the study
- Proportion of subjects (%) who prematurely discontinued from the study due to AEs

A description of the safety measures is provided in Section 7.

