3.12.3.1. Weeks 4 and 12 [Visits 3 and 4]

The following procedures/assessments will be performed at weeks 4 and 12 (visits 3 and 4):

- perform clinical laboratory tests
- perform brief physical examination
- perform ECG
- perform vital signs measurements
- urine β -HCG test for women of childbearing potential
- C-SSRS ("Since Last Visit" version)
- UHDRS-TMS
- mPPT - **at Week 12 only**
- PBA-s
- inquire about AEs
- concomitant medication inquiry (including inquiry about changes in use of benzodiazepines and antidepressants)
- inquiry about changes in use of alcohol and illicit drugs
- dispense/collect study drug
- review study compliance

3.12.3.2. Telephone Contact at Week 18 and Week 38

Patients will be contacted by telephone at week 18 and week 38 to evaluate safety and tolerability to the study drug through the following:

- assessment of adverse events
- use of concomitant medications (including inquiry about changes in use of benzodiazepines and antidepressants)
- inquiry about changes in use of alcohol and illicit drugs
- C-SSRS ("Since Last Visit" version)
- abbreviated PBA-s (a subset of PBA-s questions on depressed mood, suicidal ideation, anxiety, irritability, loss of motivation, and obsessive-compulsive behaviors)
- review of study adherence

3.12.3.3. Week 26 (Visit 5), Week 52 (Visit 6), Week 78 (Visit 7) and Week 104 (End Of Treatment, Visit 8)

The following procedures/assessments will be performed at Weeks 26, 52, 78, and 104 (s Visits 5-8):

- perform clinical laboratory tests
- perform brief physical examination
- perform ECG
- perform vital signs measurements
- urine β -HCG test for women of childbearing potential
- C-SSRS ("Since Last Visit" version)
- UHDRS-TMS
- mPPT
- UHDRS-TFC
- SF-12 questionnaire
- PBA-s
- Q-motor assessments – **at Visits 6, 7, and 8 only**
- inquire about AEs
- concomitant medication inquiry (including inquiry about changes in use of benzodiazepines and antidepressants)
- inquiry about changes in use of alcohol and illicit drugs
- dispense study drug – **only at Visits 5, 6, and 7**
- collect study drug – **at Visits 5, 6, 7, and 8**

- review study compliance

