3.12.5. Unscheduled Visits

An unscheduled visit may be performed at any time during the study at the patient's request or as deemed necessary by the investigator. The date and reason for the unscheduled visit will be recorded on the CRF as well as any other data obtained (eg, adverse events, concomitant medications and treatments, and results from procedures or tests).

Procedures performed during unscheduled visits include the following:

- concomitant medication review (including inquiry about changes in use of benzodiazepines and antidepressants)
- inquiry about changes in use of alcohol and illicit drugs
- vital signs measurements
- AE inquiry
- review of study drug accountability
- collect study drug
- study compliance review
- C-SSRS ("Since Last Visit" version) and PBA-s (if visit scheduled to assess psychiatric adverse events)

Other procedures may be performed at the discretion of the investigator.

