4.1. Patient Inclusion Criteria

Patients may be included in this study only if they meet all of the following criteria:

- a. [Revision 1] Patient has completed the PRIDE-HD trial within the last 6 months, including the follow-up period, or transitioned from Open-HART.

For patients that have failed to complete PRIDE-HD or those who completed the PRIDE-HD study over 6 months prior to the screening visit, and meet all other inclusion criteria, eligibility should be discussed with the Open-PRIDE medical monitor and clinician on a case-by-case basis.
- b. [Revision 1] For patients that experienced a drug-related SAE or had a major compliance violation during PRIDE-HD or Open-HART, eligibility approval should be discussed with PRIDE-HD's or Open-HART's medical monitor and clinician. Patients that experienced an adverse event/serious adverse event of suicidal ideation/behavior will be excluded without discussion.
- c. Able and willing to provide written informed consent prior to any study related procedure being performed. Patients with a legal guardian should be consented according to local requirements.
- d. Females of child bearing potential have to be compliant in using adequate birth control throughout the duration of the study. Adequate birth control is defined as consistent practice of an effective and accepted method of contraception according to local regulations (hormone-based, intrauterine device, or double barrier contraception, i.e., condom and diaphragm). Abstinence is an acceptable method of contraception only when this is the preferred and usual lifestyle of the subject. Periodic abstinence (calendar, symptothermal, post-ovulation methods), withdrawal (coitus interruptus), and lactational amenorrhoea method (LAM) are not acceptable methods of contraception. Male study participants have to be compliant in using adequate birth control with their partners (as defined above) throughout the duration of the study.
- e. Body weight ≥ 50 kg. Patients that meet this criterion at screening but fail to meet it at a subsequent visit may be discontinued based on Investigator or Sponsor discretion. It is allowed to repeat the weight measurement once, if clinically appropriate.
- f. Willing and able to take oral medication and able to comply with the study specific procedures.
- g. Ambulatory, being able to travel to the study center, and judged by the investigator as likely to be able to continue to travel for the duration of the study.

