7.6. Physical Examinations

Physical examinations and weight will be performed at the time points detailed in [Table 1](#).

The brief (symptom-directed) physical exam will be focused on general appearance, the cardiovascular, pulmonary, abdominal exams, as well as directed towards any patient-reported symptoms. The brief neurological exam includes observation for cerebellar (intention) tremor and for non-cerebellar tremors (eg, resting or positional), finger-nose, heel-shin, Romberg, tandem walking, positional, and gaze-evoked nystagmus.

Any physical examination finding that is judged by the investigator as a potentially clinically significant change (worsening) compared with a baseline value will be considered an adverse event, recorded on the CRF, and monitored as described in [Section 7.1.2](#).

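### No weight is scheduled at Weeks 4 and 12, although creatinine is drawn then and two Section 3.10.1 discontinuation criteria depend on weight

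*Protocol*

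**What the plan says.** Table 1 footnote f in Protocol Section 3.12 sets the weighing schedule: "Weight will be measured at the screening visit and at baseline (for study eligibility) and at week 26, 52, 78, 104 and 106". Section 7.6 adds no time points of its own and refers back to Table 1: "Physical examinations and weight will be performed at the time points detailed in". Vital signs (Table 1 footnote i and Section 7.4) are pulse, blood pressure and temperature, so they do not bring weight in.

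Laboratory testing is more frequent. Section 3.4 says: "Clinical laboratory evaluations (hematology, clinical chemistry, and urinalysis) - will be performed at each study visit". Creatinine is on the chemistry panel in Section 7.3.1. The visit list in Section 3.12.3.1, which opens "The following procedures/assessments will be performed at weeks 4 and 12 (visits 3 and 4", includes laboratory tests and a brief physical examination but does not name weight.

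Section 3.10.1 lists reasons to discontinue a patient. Two involve weight:

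- The first concerns weight itself: "their body weight decreases to <50 kg (may be discontinued based on Investigator or Sponsor discretion")
- The second concerns renal function, through a formula that contains weight: "and/or if creatinine clearance decreases to <60 mL/min (calculated using the Cockcroft-Gault equation")

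The second carries no discretionary wording. Inclusion criterion e in Section 4.1 also looks ahead to later visits: "Patients that meet this criterion at screening but fail to meet it at a subsequent visit may be discontinued", at investigator or sponsor discretion.

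**The concern.** Weeks 4 and 12 are the only on-site visits between baseline and Week 26; Week 18 is a telephone call. Study drug is dispensed at both. Both criteria should therefore be workable there, yet the schedule supplies only one of the two measurements they need.

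The 50 kg criterion has no scheduled value at either visit. The clearance criterion can be calculated, but a site following the schedule has only the baseline weight to combine with a current creatinine. Section 3.10.1 does not say whether that is intended.

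Section 1.4.3 gives low body weight (under 50 kg) and renal impairment as the conditions in which exposure to pridopidine could be high. At stake is a patient close to either limit who has lost weight since baseline. That patient can cross the limit without the Week 4 or Week 12 check showing it, and the investigator or sponsor may then have no current value on which to exercise discretion.

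**Working it through.** The plan states no figure to reproduce on this point. The check compares the schedule with the criteria and then sizes the effect.

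**Schedule**

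| On-site visit | Creatinine | Weight scheduled |
|---|---|---|
| Screening, baseline | yes | yes |
| Week 4 | yes | no |
| Week 12 | yes | no |
| Weeks 26, 52, 78, 104 | yes | yes |
| Week 106 | yes | yes |

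Weight is scheduled at 4 of the 6 on-treatment on-site visits. The two gaps are the first two.

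**Time to the next scheduled weight.** From Week 4: 26 − 4 = 22 weeks. From Week 12: 26 − 12 = 14 weeks. The ±14-day window at Week 26 can add 2 weeks to each. The first on-treatment weight can thus fall 26 + 2 = 28 weeks after baseline.

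**Clearance.** Exclusion criterion g (Section 4.2) gives the Cockcroft-Gault formula, read here as (140 − age) × weight × [0.85 if female] / (72 × serum creatinine). Clearance is proportional to weight. If a fraction L of baseline weight has been lost, using the baseline weight overstates clearance by 1/(1 − L) − 1. A reading of 60 on the baseline weight is 60 × (1 − L) on the current weight, so the band missed below the limit is 60 × L wide. The losses below are assumptions, because the documents give no rate.

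| Assumed loss L | Overstatement | True value when the reading is 60.0 | Missed band |
|---|---|---|---|
| 2% | 1/0.98 − 1 = 2.0% | 58.8 mL/min | 1.2 mL/min |
| 5% | 1/0.95 − 1 = 5.3% | 57.0 mL/min | 3.0 mL/min |
| 10% | 1/0.90 − 1 = 11.1% | 54.0 mL/min | 6.0 mL/min |

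**Illustration (assumed patient).** A man aged 50 has a creatinine of 1.2 mg/dL. At a baseline weight of 60 kg: 90 × 60 / (72 × 1.2) = 62.5 mL/min, above the limit. At 57 kg, a 5% loss: 90 × 57 / 86.4 = 59.4 mL/min, which meets the criterion. The blood result is the same in both cases.

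**Weight limit.** The loss that brings a patient to 50 kg is 1 − 50/baseline weight.

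| Baseline weight | Loss to reach 50 kg |
|---|---|
| 51 kg | 2.0% |
| 52 kg | 3.8% |
| 55 kg | 9.1% |

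A larger loss takes the patient below 50 kg, and no scheduled measurement would show it before Week 26.

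**The case against.** The strongest reply is that this is a deliberate and consistent monitoring interval. From baseline to Week 104, weights fall every 26 weeks, and the carried-forward weight is only about 4 weeks old at Week 4 and 12 weeks old at Week 12. That is fair as a description. It does not explain why these two visits alone pair a creatinine with no scheduled weight.

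The second reply is that nothing prevents a site from weighing a patient who is already there. A brief examination takes place at both visits, the 50 kg criterion is discretionary, and Section 3.12.5 says of unscheduled visits: "Other procedures may be performed at the discretion of the investigator". This stands as a limit on the harm, but an optional weighing is not a planned check.

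Third, other safeguards operate at the same visits without any weight: the QTcF rule above 500 msec, the hypokalemia rule, and creatinine itself. De-escalation to 22.5 mg bid is also possible. All of these stand and reduce the consequence.

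Fourth, the assumed losses are hypothetical. Nothing in the documents supports a 10% loss within 12 weeks, and at 2% the missed band is only 1.2 mL/min. This stands too.

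Two narrower points are also right. The silence of Section 3.12.3.1 proves little, since the lists for baseline, Weeks 26 to 104 and Week 106 do not name weight either; footnote f decides the matter. And SAP Section 7.5 plans weight summaries at baseline and every visit, while SAP Section 2.1 describes up to 650 patients against the Protocol's 300. The SAP may therefore rest on a later schedule, which cannot be checked from these documents.

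**Conclusion.** The concern holds for the protocol supplied. Weight is not scheduled at Weeks 4 and 12, creatinine is, and Section 3.10.1 does not say which weight enters the clearance calculation.

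The effect is small and confined to patients near a limit. Under assumed losses of 2% to 10%, the clearance check misses patients whose true value is at most 1.2 to 6.0 mL/min below 60. The weight check misses those who start slightly above 50 kg and lose enough to cross it. Patients well above both limits are unaffected. No efficacy estimate or planned analysis method is in question. This is an optional, low-cost improvement to safety monitoring.

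**What to change.** Add Weeks 4 and 12 to Table 1 footnote f, and name weight in the Section 3.12.3.1 list. Naming it in the other post-screening lists as well would keep them consistent. In Section 3.10.1, state that Cockcroft-Gault clearance uses the weight measured at the same visit as the creatinine.

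The cost is protocol wording and two extra weighings per patient, at visits that already include an examination and a blood draw. A few more patients near the limits may be flagged, which is the purpose of the criteria.
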